# Hypotheses

It is hypothesised that:

- i. Those who walk the furthest will have lower exertional dyspnea scores during the 6MWT.
- ii. Exertional dyspnea will increase with an increase in gradient of the dyspnea challenge.
- iii. There will be differences between the two tests; there will be no-steady state response in the dyspnea challenge when compared to the 6MWT, a higher peak VO2 response and a marked difference in oxygen saturation.
- iv. The dyspnea challenge is able to detect both acute and longer term changes in exertional dyspnea as a result of interventions.

## Methods

## a. Study Design

The research study will be a prospective, randomised, controlled, single-blind trial (Fig. 1). This is a multi-centre study where the outcome measurements will be conducted at The Prince Charles Hospital, Griffith University, Gold Coast Campus, Bundaberg Health Promotions and Central Queensland University, Bundaberg Campus. Ethics approval will be sought before commencement from the Metro North Health HREC B and Griffith University (GU) Human Research Ethics Committees (HREC).

[figure not shown]

Figure. 1: Study schematic

## b. Study Setting

The study will be undertaken at the TPCH, GU Gold Coast Campus, Bundaberg Health Promotions and Central Queensland University Bundaberg Campus. Participants will be recruited from the Gold Coast University Hospital, The Prince Charles Hospital and Bundaberg Health Promotions. Data collection will take place at: Griffith University Gold Coast Campus (GO2, 2.41 or G40 4.16), the Prince Charles Hospital rehabilitation gymnasium, Bundaberg Health Promotions gymnasium or Central Queensland University Bundaberg campus (building 1, Physiotherapy gymnasium). The principle researchers at the Prince Charles Hospital are: [name] (Exercise Science), [name] (Physiotherapist), [name] (Physiotherapist) and [name] (Physiotherapist). At Bundaberg Health Promotions: [name] (Physiotherapist), [name] (Medical Doctor). At Central Queensland University: [name]. At Griffith University: [name], [name] (Exercise Physiology), [name], [name] (Exercise Science). At the Gold Coast University Hospital: [name] (Medical Doctor Respiratory Medicine) and [name] (Physiotherapist).

## c. Study Population

Thirty individuals with COPD, thirty with heart failure and thirty with pulmonary hypertension will be recruited into the study if they meet the following criteria:

- A known diagnosis COPD, heart failure or pulmonary hypertension.
- Completed the Gold Coast Health pulmonary or cardiac rehabilitation Program.
- Completed the Prince Charles Hospital pulmonary or cardiac rehabilitation Program.
- Completed the Bundaberg Health Promotions cardiac or pulmonary rehabilitation program.
- Are clinically stable and are on firm, optimised respiratory or cardiac therapy for six weeks before enrolment.
- Global Initiative for Chronic Obstructive Lung Disease (GOLD) categories I-IV.
- New York Heart Association (NYHA) for Heart Failure categories I-III.
- World Health Organisation (WHO) for Pulmonary Hypertension categories I-III.
- Aged  $\geq$  18 years old.

#### **Exclusion Criteria:**

- Musculoskeletal disorders that prevent walking on the treadmill.
- Significant co-morbidities that would exclude exertional exercise or any contraindications to exercise as defined by the American College of Sports Medicine.
- Oxygen therapy that would exclude the wearing of portable metabolic cart.
- Chest wall binder Part C of study only Extensive cardiac history and/or untreated high blood pressure.

#### d. Recruitment and Consent

- Individuals with COPD, heart failure and pulmonary hypertension will be recruited from the Gold Coast University Hospital, The Prince Charles Hospital and Bundaberg Health Promotions cardiac or pulmonary rehabilitation program.
- Those recruited from the Gold Coast University Hospital site will complete data collection at the Griffith University Gold Coast campus exercise science laboratories. Those recruited from The Prince Charles Hospital site will complete the study on-site in the physiotherapy gym. Those recruited from the Bundaberg Health Promotions rehabilitation program will undertake data collection at either the on-site gymnasium facility or Central Queensland University, Bundaberg campus physiotherapy laboratories.
- Any individual deemed appropriate for the study will be approached by the treating physiotherapist to be made aware of the study. If interested, a researcher will explain the study in more detail. Interested individuals will then be screened against the inclusion criteria. Those who meet the eligibility criteria and are interested in participating in the research will be provided with the participant information sheet, which includes the contact information of the research team, by the treating clinician.
- If the potential participant wishes to participate, one of the study investigators will discuss the study with the potential participant via the informed consent process.
- Once all information has been given a participant will be given a cooling-off period of 48 hours to consider participation if required. Participants will also be assured of withdrawal rights even after informed consent has been obtained.
- The consent process will be respectful and acknowledge the cultural and linguistic diversity of the participants, as well as various levels of understanding and literacy issues. Provisions will be put in place including the use of an interpreter service for participants

whose primary language is other than English. We will also adapt our explanations and provide support with conveying the content of the participant information and consent form to cater for various levels of understanding and literacy issues.

## a. Participant confidentiality

Information will be stored during the research project in paper copy format (i.e. medical records, investigation reports, research paperwork) in a regulatory binder and electronic format (i.e. excel spreadsheet on hard drive). Only site staff (i.e. principal and co-investigators) will have direct access to medical records and study-specific related documentation. This information will be stored in locked cabinets in a secure location at TPCH, Central Queensland University or GU all of which require 24-hour key card access. Information will be stored in electronic format on computers with site-specific security precautions, i.e. password-protected database on a password-protected computer in a secure office within TPCH, Central Queensland University and GU.

Once the relevant data has been extracted and linked, the electronic data will have all identifiable information removed so that the data file that is to be analysed and stored will be non-identifiable. A copy of the non-identifiable data file will be provided to other members of the research team at GU, TPCH, Bundaberg Health Promotions and Central Queensland University so that they can assist with the data analysis, which will be securely deleted once the analysis and reporting phase of the research study is completed. The study information will be kept for a minimum of 5 years post completion of the study as per the NHMRC guidelines.

Results obtained from the study will be presented to all participants in a written report. All data will be represented as group averages, and no participant will be able to be identified. Participants will also be able to access any published documents resulting from the project.

## b. Participant safety

There is a potential risk of participants experiencing an adverse event or reaction with the outcome measurements and exercise tests during the study. These may include angina, presyncope or syncope, dysrhythmias, physical pain or discomfort, and musculoskeletal injury. This risk is inherent with undertaking any exertional activities including the outcome measures such as the six-minute walk test and the dyspnea challenge. However, these risks will be mitigated by ensuring a comprehensive assessment and screening of participants and close monitoring during the outcome measurements. We will only use participants who have been medically cleared to complete a rehabilitation program and have been deemed safe to exercise by their medical team. We will also adhere to the standard precautions and contraindications for exercise testing in COPD, heart failure and pulmonary hypertension patients as per the ERS and ATS guidelines [26, 27]. All investigators have completed basic life support and first aid training in addition, there will be at least one investigator trained in the use of oxygen and defibrillation present or near-by. The settings for data collection (Prince Charles Physiotherapy gymnasium and Griffith University G40 Laboratories 1.16, Central Queensland University, building 1 Physiotherapy and Bundaberg Health Promotion rehabilitation gymnasium) are equipped with medical oxygen and an automated defibrillator. The supervisors of the project are highly experienced in supervising exercise tests in chronic disease.

Adverse events during the study will be determined as outlined by the National Health and Medical Research Council (NHMRC, 2016) definition, i.e. "Any untoward medical occurrence

in a patient or clinical trial participant administered a medicinal product, and that does not necessarily have a causal relationship with this treatment" (26). The participant will also be monitored for any adverse reactions as per the NHMRC (2016) definition, i.e. "Any untoward and unintended response to an investigational medicinal product related to any dose administered" (26). In addition, serious adverse events or adverse reactions will be defined as "Any adverse event/adverse reaction that results in death, is life-threatening, requires hospitalisation or prolongation of existing hospitalisation, results in persistent or significant disability or incapacity" (NHMRC, 2016) (26). The adverse event log document will be used to keep a detailed record of such incidences, with appropriate action taken as required. All serious adverse events will be reported to all associated HRECs within 24 hours.

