## d. Study Procedure

Participants may be required to complete all three parts of this study, there are a total of nine visits over the three parts. Visits 1-3 will address question one and investigate the ability of the 6MWT and its outcome measure of six-minute walk distance (6MWD) to act as a surrogate measure of exertional dyspnea (ED). The secondary outcomes are to non-invasively monitor cardiopulmonary factors to compare the metabolic costs of both tests and compare this across disease population. Visits 4-6 will address question two and consider the sensitivity of the dyspnea challenge in heart and lung disease groups by asking individuals to perform the dyspnea challenge at differing gradients ranging from 3 to 8%. Visits 7-9 will address question four and secondary aim seven to assess the responsiveness of the dyspnea challenge in heart and lung disease groups by asking individuals to perform the dyspnea challenge pre and post an intervention that has proven to increase or decrease dyspnea. There will be an acute challenge using a chest wall binder that will be applied only to COPD participants which is known to increase dyspnea and then a longer term intervention being that of Pulmonary and Heart Failure Rehabilitation which is known to improve dyspnea in the COPD and HF populations. Participants will complete two dyspnea challenges pre and post the exercise rehabilitation programs which will be completed outside of this study. Participants included in the acute challenge part of the study will complete the dyspnea challenge in random order on two separate visits with and without a chest wall binder fitted.

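### The adverse event and adverse reaction definitions are drug-trial wording that does not fit a study giving no medicinal product, and they conflict with the test-related risks the same section names

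*Protocol*

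**What the plan says.** All the relevant rules stand in the Protocol, section b. Participant safety. It opens with the risk the authors have in mind: "There is a potential risk of participants experiencing an adverse event or reaction with the outcome measurements and exercise tests during the study". It then lists angina, presyncope or syncope, dysrhythmias, pain or discomfort, and musculoskeletal injury, and attributes the risk to exertion in the six-minute walk test (6MWT) and the dyspnea challenge.

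The operative rule follows: "Adverse events during the study will be determined as outlined by the National Health and Medical Research Council (NHMRC, 2016) definition". The definition quoted there covers an untoward medical event "in a patient or clinical trial participant administered a medicinal product", and closes by saying that a causal link with the treatment is not required. An adverse reaction is "Any untoward and unintended response to an investigational medicinal product related to any dose administered". A serious event is "Any adverse event/adverse reaction that results in death, is life-threatening, requires hospitalisation or prolongation of existing hospitalisation", with lasting disability or incapacity also included.

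Two actions depend on these definitions. For the log: "The adverse event log document will be used to keep a detailed record of such incidences". For the ethics committees: "All serious adverse events will be reported to all associated HRECs within 24 hours".

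Section d. Study Procedure describes what participants undergo. On the acute intervention it says: "There will be an acute challenge using a chest wall binder that will be applied only to COPD participants". The longer-term intervention is exercise rehabilitation, delivered outside the study. No study drug appears in Parts A, B or C.

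**The concern.** Both definitions depend on a medicinal product and the study gives none. A syncope on the treadmill, or an untoward response to the binder, is the kind of event the section says it wants to catch, yet the definitions do not describe it. The serious category is made up of adverse events and adverse reactions, so it inherits the same condition. The log and the 24-hour report then inherit it too.

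What is at stake is consistent capture. Data are collected at several sites (sections a. Study Design and b. Study Setting). If the definition does not fit the study, each site has to supply its own, and sites may differ in what they log. The protocol also does not say how an event linked to the challenge or the binder is to be classed.

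**Working it through.** No calculation applies, and the protocol gives no figure to reproduce. The check is to follow the chain of definitions and compare each link with what the study does.

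1. **Does the study administer a medicinal product?** Visits 1 to 3 (Part A) contain questionnaires, spirometry, 6MWTs and dyspnea challenges. Visits 4 to 6 (Part B) contain dyspnea challenges at several gradients. Visits 7 to 9 (Part C) contain dyspnea challenges with and without a binder, then challenges after rehabilitation. Monitoring is non-invasive throughout. The answer is no: there is no investigational product and no dose.

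2. **Adverse reaction.** The definition needs an investigational medicinal product and a dose of it. Neither exists, so no event in this study can qualify, however clearly a walk test or the binder caused it.

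3. **Adverse event.** The definition needs a participant given a medicinal product. It does not say investigational. Its closing words on causality refer back to that product as the treatment, which points to something given by the trial. On that natural reading, test-related events fall outside.

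4. **Serious event.** This is an adverse event or an adverse reaction that also meets a seriousness criterion. The adverse reaction route is closed by step 2. The adverse event route is open only as far as step 3 allows.

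5. **Log and report.** The log covers the events just defined, serious or not. The 24-hour rule covers serious adverse events only. Both take their scope from steps 2 to 4.

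6. **Comparison with stated intent.** The opening of the same section calls events from the outcome measurements and exercise tests adverse events or reactions. Steps 2 and 3 do not cover them as written. The two parts of the section conflict.

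7. **Can the reader recover a better definition elsewhere?** No other section gives one tied to a procedure or device. The definitions carry citation number 26, but entry 26 in section j. References is a technical standard on field walking tests, and no National Health and Medical Research Council document is listed.

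For context only, a COPD participant who completes every part does 1 + 2 + 6 + 4 + 2 = 15 dyspnea challenges (Visit 1, Visits 2–3, Visits 4–6, Visits 7–8, Visit 9) and 1 + 2 = 3 six-minute walks. This counts exposure to the procedures the definitions do not mention. It does not count missed events.

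**The case against.** The strongest reply concerns the adverse event definition. Unlike the adverse reaction definition, it does not require an investigational product. Section c. Study Population requires participants to be on stable, optimised respiratory or cardiac therapy, which may well include medicines. The condition about a medicinal product may also attach only to trial participants and leave patients unrestricted. On either reading, a treadmill syncope can be an adverse event. Since a serious event may arise through either route, the log and the 24-hour report would then work.

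This stands in part. A reader might infer that no event can be captured, or that none of the 90 participants can meet the definition. The text does not support that: only the adverse reaction definition is certainly empty. But the looser reading makes capture turn on drugs the study does not give, and it does nothing to link an event to the tests or the binder.

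A second reply is that the opening of the section makes the intent plain, so staff would log these events anyway. That is likely, and nothing in the protocol shows that events would go unrecorded. But the rule as written should not need staff to set it aside.

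A third reply is that no planned result is affected. That stands. Safety is not among the aims, hypotheses or outcome measures, so a reader who infers damage to a planned safety analysis goes beyond the document. Nor does the protocol describe judging each event's relatedness against a dose, so it cannot be said that a planned attribution step would fail.

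**Conclusion.** The point holds as a conflict within section b. Participant safety. The adverse reaction definition cannot be met by any event in this study. The adverse event definition, on its natural reading, excludes the exercise-test events the section itself expects. A looser reading admits some of them, but without tying them to a study procedure. Because the serious category, the log and the 24-hour report rest on these definitions, capture depends on staff following the evident intent in place of the words.

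The conclusion rests on two things: that Parts A to C are a complete account of what the study gives, and that the closing reference to treatment in the adverse event definition means a trial product. The first is clear from the text. The second is the more natural reading but not the only one. The defect is worth correcting because it sits in a safety rule and is cheap to mend. It does not touch the efficacy design or any planned estimate.

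**What to change.** Reconcile the two parts of section b. Participant safety by replacing the quoted definitions:

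- **Adverse event:** any untoward medical event in a participant during study participation, whether or not it is related to a study procedure.
- **Adverse reaction:** an adverse event judged related to a study procedure or device (6MWT, dyspnea challenge or chest wall binder).

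Leave the seriousness criteria and the 24-hour reporting rule unchanged. Correct the citation attached to the definitions at the same time. The cost is one paragraph of protocol wording and slightly more events logged.

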## c. Participant withdrawal from the study

Participants will be advised that they may withdraw from the study at any time without any implications for their care or relationship with the. The participant will be requested to notify us, if possible, prior to withdrawing from the study and to complete the 'Participant Withdrawal of Consent Form' as part of the PICF. Participants will also be withdrawn from the study if they have a significant adverse event or change in their medical status and it is deemed unsafe for them to continue with the investigation. At the time of withdrawal, it will be ascertained from the participant whether they will allow the continued collection and use of their information by the researchers. If they do not permit this, their data will be securely disposed or deleted from the data file.

## d. Study Procedure

Participants may be required to complete all three parts of this study, there are a total of nine visits over the three parts. Visits 1-3 will address question one and investigate the ability of the 6MWT and its outcome measure of six-minute walk distance (6MWD) to act as a surrogate measure of exertional dyspnea (ED). The secondary outcomes are to non-invasively monitor cardiopulmonary factors to compare the metabolic costs of both tests and compare this across disease population. Visits 4-6 will address question two and consider the sensitivity of the dyspnea challenge in heart and lung disease groups by asking individuals to perform the dyspnea challenge at differing gradients ranging from 3 to 8%. Visits 7-9 will address question four and secondary aim seven to assess the responsiveness of the dyspnea challenge in heart and lung disease groups by asking individuals to perform the dyspnea challenge pre and post an intervention that has proven to increase or decrease dyspnea. There will be an acute challenge using a chest wall binder that will be applied only to COPD participants which is known to increase dyspnea and then a longer term intervention being that of Pulmonary and Heart Failure Rehabilitation which is known to improve dyspnea in the COPD and HF populations. Participants will complete two dyspnea challenges pre and post the exercise rehabilitation programs which will be completed outside of this study. Participants included in the acute challenge part of the study will complete the dyspnea challenge in random order on two separate visits with and without a chest wall binder fitted.

#### Part A:

Visit 1 – Familiarisation will be split into three parts; 1) participant information/consent and health assessment, 2) pulmonary function testing (PFT) and 3) exercise testing. 1) Participants will enter the laboratory and the full extent of the study, both part A, B and C, will be explained with the aid of the information sheet. If the participant is happy to proceed, voluntary consent will be obtained followed by the completion of a health screening assessment and the St George Respiratory questionnaire (SRGQ) for COPD participants or Kansas City Cardiomyopathy Questionnaire for heart failure participants, the medical research council (mMRC) questionnaire, Dyspnoea-12 questionnaire, and a hospital anxiety and depression (HADS) questionnaire to summarise the impact of disease and dyspnea on their overall health status. 2) PFT – resting blood pressure and forced spirometry (Medikro Spirostar 2000, Medikro Oy, Kuopio, Finland) will be measured according to standard protocols[28]. 3) familiarisation testing will be performed for both a six-minute walk test (6MWT) and the 2-minute dyspnea challenge (DC). Each subject will be informed of the safety precautions, including criteria for safely terminating an exercise test (per the American College of Sports Medicine Guidelines for Exercise Testing and Prescription, 2009).

The 6MWT will be performed using a standardised protocol [29]. Participants will walk along a long, flat, straight, temperature-controlled corridor on a course measuring 30 metres. The turnaround points will be marked by black tape along the floor. Each participant will be asked to walk as far as possible with only standardised encouragement given. Pulmonary gas exchange (Metamax, Cortex BXB, Lepzig, Germany), cardiac output (PhysioFlow, Manatec Biomedical, Paris, France), and muscular tissue oxygen saturation of the gastrocnemius (PortaMon Artinis Medical Systems, Einsteinweg, The Netherlands) will be monitored continuously throughout the protocol. After each minute, the severity of dyspnoea, (modified 0-10 Borg Scale), heart rate and forehead oxygen tissue saturation (RAD-5v Masimo Corp, Irvine, CA, USA) will be recorded. At the end of the test, sensory and affective measures of ED will be assessed using a Multidimensional Dyspnea Profile (MDP)[30].

The DC will be performed be on a treadmill in a temperature-controlled laboratory. Participants will walk on a treadmill for 2-minutes at a speed of 3km/h and a gradient of 4%. Perrault *et al.*, [17] found that 93% of patients suffering from moderate-severe COPD managed to complete a 3-minute walk test at 1.5km/h on a flat surface and that only 84% managed to complete the test at 2.5km/h. The gradient selected was chosen as previous research in 8 participants with mild COPD managed to achieve a 2-minute challenge at between 4-6% gradient[25]. Electrocardiogram (ECG), Heart rate (HR) and oxygen saturation (SpO2) will be monitored continuously using a portable saturation monitor (RAD-5v Masimo Corp, Irvine, CA, USA). Ratings of ED will be participant self-reported every 10 seconds using a 0-10 Numerical Rating Scale (NRS) on a PC-based system with a computer monitor mounted in front of the treadmill. Pulmonary gas exchange (Metamax, Cortex BXB, Lepzig, Germany), cardiac output (Q) (PhysioFlow, Manatec Biomedical, Paris, France) and muscle tissue oxygen saturation (MtO2) (PortaMon Artinis Medical Systems, Einsteinweg, The Netherlands) will be monitored continuously. At the end of the test, sensory and affective measures of ED will be assessed using the MDP[30].

Visit 2 and 3 – During these two visits, participants will perform 2x6MWT and 2xDC. These tests will be performed in a randomised order with 30 minutes of rest in between. 1x6MWT and 1xDC will be performed as above with the same equipment and measures assessed. The other two tests they will be performed without the pulmonary gas exchange measures being assessed. This is to negate the impact of the face mask on self-perceived ratings of exertional dyspnea. During these two tests, ECG, Q, MtO2, HR, SpO2, and blood pressure will be monitored as above. At the end of each test the MDP will be performed.

